Appendix VIII – Tanzania MoHCDGEC Male Circumcision Client Form

THE UNITED REPUBLIC OF TANZANIA
MINISTRY OF HEALTH, COMMUNITY DEVELOPMENT, GENDER, ELDERLY AND CHILDREN

VOLUNTARILY MEDICAL MALE CIRCUMCISION
INDIVIDUAL CLIENT RECORDS

CLIENT PROFILE

1. Name of health facility or MC site _____
2. Service Delivery Approach Static / routine Outreach/mobile/campaign
3. Client's Name: _____ Phone _____
4. Client ID Number _____
5. Client's Address:
Region _____
District _____
Ward _____
Village _____
Age years _____
6. Marital status: Married Single Cohabiting Not applicable (minor)
7. Visit Date:
d d m m y y y y

COMING FROM

Self-referred	
VCT	
PITC	
Other (please describe)	

MEDICAL HISTORY

8. Has the client had any STIs in the last 3 months? Yes No
9. Does the client currently have any of the following complaints?
 - a. Urethral discharge: Yes No
 - b. Pain on erection: Yes No
 - c. Pain on urination: Yes No
 - d. Genital warts: Yes No
 - e. Genital sore (ulcer): Yes No
 - f. Swelling of the scrotum: Yes No
 - g. Difficulty in retracting foreskin: Yes No
 - h. Others: _____

10. Is client under treatment for any of the following?

CONDITION	DIAGNOSED (Y/N)	ON MEDICATION (Y/N)
Hypertension	Yes  No 	Yes  No 
Diabetes	Yes  No 	Yes  No 
HIV/AIDS:	Yes  No 	Yes  No 
Others (eg. TB) _____		

11. Has client ever had any surgical operation? Yes No

12. Any complications related to previous surgery? Yes No (If yes specify)

a. Infection

b. Excessive bleeding

c. Other _____

13. Any history of bleeding problems in self or family members? Yes No

14. Any known allergies to any of these medications:

a. Local Anesthetics: Yes No

b. Antiseptics: Yes No

c. Any other medications (specify) _____

15. Any history of Tetanus vaccination? Yes No Don't Know

d. Date of most recent tetanus booster _____

e. Verified by vaccination record? Yes No

PHYSICAL EXAMINATION

16. Any significant physical abnormality on general examination? Yes No

If yes, specify _____

17. Weight _____ Kg: Vital signs before procedure: Pulse rate: _____ beats/min

Blood pressure: _____ / _____ mmHg Temperature: _____ (°C)

18. Penile examination (tick):

a. Urethral discharge Yes No

f. GUD Yes No

b. Smegma under the foreskin Yes No

g. Phimosis / paraphimosis Yes No

c. undescended testicles Yes No

h. Adhesion of Prepuce to glans Yes No

d. Condylomata lata/ acuminate Yes No

i. Balanitis/redness/swelling of foreskin/ glans/ shaft Yes No

e. Hydrocele Yes No

j. Chordae (banana shaped penis) Yes No

k. Other (specify) _____

19. Client medically cleared for MC procedure? Yes No If no, why? _____

HIV TESTING

20. Client tested for HIV as part of MC service Yes No

21. Date of testing:
d d m m y y y y

a. Test result: Negative Positive Indeterminate

CLIENT REFERRED TO

22. a. STI b. Other surgical/medical c. CTC d. psychosocial support e. client not referred

INFORMED CONSENT FOR MALE CIRCUMCISION PROCEDURE

I _____ have agreed and consented for you to do the operation of Circumcision (removal of the foreskin) on me/my child. I understand that Male Circumcision is a surgical procedure and with any medical or surgical procedure there are risks involved.

I have read/ had it read and understood this consent form. I have been given enough information and a chance to ask questions and all my questions about male circumcision have been answered in a satisfactory manner.

I am the parent _____ legal guardian _____ (*tick the relationship for MC procedure on minor). My signature below indicates that I have freely given permission for me/my child to have Male Circumcision performed.

Thumbprint/signature of
client/parent/guardian

Signature MC
provider/counsellor

Date

MC PROCEDURE

23. MC procedure conducted Yes No

24. Date of MC procedure
d d m m y y y y

Time Started _____ Time Finished _____

25. Anaesthesia Used: Lignocaine _____ ml _____ % Bupivacaine: _____ ml _____ %
Other _____ ml _____ %

26. Method: Forceps-guided Dorsal Slit Sleeve Resection

Surgeon's Name: _____ Cadre: _____

Assistant's Name: _____ Cadre: _____

Additional Notes (if needed): _____

27. Intraoperative AE: Any adverse event occurrence during procedure? Yes No If yes tick type of AE below..

- a. excessive skin removal Yes No
- b. damage to penis Yes No
- c. excessive bleeding Yes No
- d. anesthetic-related event Yes No
- e. other

28. Severity of intraoperative AE:

- a. Mild
- b. Moderate
- c. Severe

POST-OP AND DISCHARGE

29. Please describe the condition of the bandage in relation to bleeding:

a. Bandage clear b. Blood spot on bandage c. Bandage soaked

30. Vital Signs after procedure:

Pulse rate: _____ beats/min c. Blood pressure: _____ / _____ mmHg d. Body temperature _____ (°C)

31. General condition at discharge:

Satisfactory b. Needs follow up c. Not discharged

32. Analgesics given Yes No Type and dosage given. Specify _____

FOLLOW-UP NOTES

Date of first follow up visit:
d d m m y y y y

Days post-op: _____

Notes: _____

Did a post-operative AE occur? Yes No

If AE occurred, date of AE

d d m m y y y y

Condom given Yes No

Quantity given _____

Date of Second follow up visit:
d d m m y y y y

Days post-op: _____

Notes: _____

Did a post-operative AE occur? Yes No

If AE occurred, date of AE

d d m m y y y y

Condom given Yes No

Quantity given _____

POST OPERATIVE AE BY TYPE

Type of AE at first follow up visit:

(i) a. Bleeding or blood soiling of the BANDAGE Yes No
b. Swelling of the penis or scrotum Yes No
c. Persistent pain Yes No
d. Infection Yes No
e. Failure to pass urine Yes No
f. Other: Specify _____

(ii) Severity, post-operative adverse event

Mild Moderate Severe

Type of AE at Second follow up visit:

(i) a. Bleeding or blood soiling of the BANDAGE Yes No
b. Swelling of the penis or scrotum Yes No
c. Persistent pain Yes No
d. Infection Yes No
e. Failure to pass urine Yes No
f. Other: Specify _____

(ii) Severity of post-operative adverse event

Mild Moderate Severe

Other AEs Occurred after 7 days Date: _____

Appendix IX – Case Report Form (CRF) – ShangRing Device

CASE REPORT FORM – ShangRing DEVICE

Evaluation of the safety and acceptability of the ShangRing device for male circumcision in Tanzania

Site Code:

Client ID # (CID):

INSTRUCTIONS FOR THE PROPER COMPLETION OF THE CRF

Please follow the instructions below:

1. Use a ball-pen, DO NOT use a pencil, a marker or a fountain pen.
2. Make sure to place the separator provided under the last copy of each page so that data recorded on one page does not copy to the next.
3. Subject initials will be comprised of the first letter of the first name followed by the first two letters of the surname.
4. Fill in the form in a clear, concise and readable way. Use common medical terminology.
5. Correct wrong data by crossing out the information with a single line and writing the correct data next to it. The evaluation coordinator, or the site coordinator in the evaluation coordinator's absence, will initial and date the correction.
 - a. Example: 07/03/1969 corrected to 09/03/1969 (with initials and date of the correction)
6. Complete all the available boxes, DO NOT leave empty fields.
 - a. For evaluations not performed record ND (not done).
 - b. For data not relevant to the subject or stage of evaluation record NA (not applicable).
 - c. If you do not know the data, please use the initials UNK (unknown).
 - d. Use leading zeroes if necessary (e.g.: 15 mg = 0 1 5 mg).
 - e. Make sure to complete every header on each page.
7. Please make sure to **circle the correct option** whenever it is requested.
8. Please DO NOT add wording to CRF pages unless required. For any additional comments please use the Comments Sheet at the end of the CRF modules.
9. Dates (e.g., date of birth, date of visit) will be recorded in the DD/MM/YYYY format.
 - a. Example: 19 June 2017 will be recorded as 19/06/2017
10. CID is the Client Identification Number. It comprises the initials of the site followed by the four digit enrollment date and the three digit subject consecutive number. Example: Subject number 1 in Good Hope Health Center enrolled on July 21 will be GH2107001.
11. Time will be recorded in 24:00 format.
 - a. Example: 6:15 pm will be recorded as 18:15

Ministry of Health, Community Development, Gender, Elderly and Children

ShangRing Device Case Report Form (Attach form to VMMC Client Form)

Part 1 – Client Eligibility and Consent

Client ID Number: _____ Date of Visit (dd-mm-yyyy): _____

Client is eligible for ShangRing circumcision (circle one)? Yes No If No, Specify Reason: _____

Confirmation of client's eligibility (circle one):

1. In good health: Yes No
2. Counseled: Yes No
3. Consented: Yes No N/A (13-17 years old)
4. If 13-17 year-old client, consent by parent/guardian and assent by client: Yes No N/A

If 'No' for any of the above, explain: _____

Part 2 – ShangRing Device Placement Procedure

Device size: _____ Expiration Date (dd-mm-yyyy): _____

If the device application is not the same day as the screening report, has there been a change in the genitals (compare to screening visit report)? Yes No

Time placement procedure began (e.g. 14:30): _____

Time placement procedure ended (e.g. 14:45): _____

Comments: _____

Was the device applied according to its Instructions for Use (circle one)? Yes No

If "No," explain in detail: _____

Was the penis disinfected before applying the device (circle one): Yes No

What form of anesthesia was used? Indicate injection/cream, what kind for each, and for injection provide dosage: _____

Please Attach ShangRing Label Here:

Was there an Adverse Event during placement (circle one)? Yes No

If yes, how would you rate the AE (circle one, refer to definitions below): Mild Moderate Severe

Severity cannot be classified (if problem with placement or device malfunction)

Adverse Event Definitions:

Mild: classification indicates minimal or no intervention is required beyond reassurance and observation

Moderate: classification relates to those AEs that are neither mild nor severe, require intervention, and are usually managed on site

Severe: classification requires extensive intervention with referral or specialist input

NB: If any Moderate, Severe, or Severity not classified adverse events above are checked, complete the AE form.

Full name and surname of clinician placing device: _____

Signature: _____ Cadre (e.g. physician, nurse): _____

Full name and surname of assistant: _____

Signature: _____ Cadre (e.g. physician, nurse): _____

Part 3 – Post-Application Evaluation and Assessment (Before Discharge)

Dressing intact and holding penis against abdomen (circle one)? Yes No

Client given post-procedure written instructions (circle one)? Yes No

Clinical disposition of client, including AE management: _____

Oral analgesia given (circle one)? Yes No Drug (name, dose, quantity dispensed): _____

Scheduled removal date (dd-mm-yyyy): _____

Discharged by (Full name and surname): _____

Signature: _____ Cadre (e.g. physician, nurse): _____

Appendix X – ShangRing Post-Placement Survey

ShangRing Post-Placement Survey

[Table to be completed by Evaluation Staff]

Date (dd/mm/yyyy):	
Client ID:	
Name of Survey Administrator:	
Facility:	

Introduction: Thank you for agreeing to complete this survey to evaluate your experience with the ShangRing circumcision device. This survey asks a few brief questions about your experience in having the ShangRing device placed. Your name will not be recorded anywhere on this survey, and your replies will be kept completely confidential. In this survey there are no right or wrong answers. We are most interested in your honest opinions and reactions to these questions. You may also refuse to answer any question you wish for any reason. The information that you provide will help to determine the future use of ShangRing in Tanzania. If you have any questions about the survey, please do not hesitate to follow up with evaluation staff. If you have difficulty reading or understanding any of the questions, evaluation staff are on hand to read and help you interpret the questions.

1. Why did you choose to have a ShangRing circumcision instead of surgical circumcision (circle answer option below)?

I thought ShangRing would be less painful	I didn't want an injection	I had heard about ShangRing before	No Reason	Other (comment below)
Comment: _____				

2. How did you find the placement process for the ShangRing device (circle answer option below)?

It was about what I expected	It was easier than I expected	It was harder than I expected	I did not have any expectations for the placement	Other (comment below)
Comment: _____				

3. How did you find the pain of your circumcision during the ShangRing device placement (circle answer option below)?

It was about what I expected	It was less painful than I expected	It was more painful than I expected	I did not have any expectations about pain	Other (comment below)
Comment: _____				

4. At this point, would you recommend the ShangRing to someone you know who is considering circumcision (circle answer option below)?

Yes	No	I don't know at this time	Other (Comment below)
-----	----	---------------------------	-----------------------

Comment: _____

Appendix XI – ShangRing Post-Removal Survey

ShangRing Post-Removal Survey

[Table to be completed by Evaluation Staff]

Date (dd/mm/yyyy):	
Client ID:	
Name of Survey Administrator:	
Facility:	

Introduction: Thank you for agreeing to complete this survey to evaluate your experience with the ShangRing circumcision device. This survey asks a few brief questions about your experience with ShangRing now that the device has been removed. Your name will not be recorded anywhere on this survey, and your replies will be kept completely confidential. In this survey there are no right or wrong answers. We are most interested in your honest opinions and reactions to these questions. You may also refuse to answer any question you wish for any reason. The information that you provide will help to determine the future use of ShangRing in Tanzania. If you have any questions about the survey, please do not hesitate to follow up with evaluation staff. If you have difficulty reading or understanding any of the questions, evaluation staff are on hand to read and help you interpret the questions.

1. How much discomfort did you experience while wearing the ShangRing device over the past seven days (circle answer option below)?

I had no discomfort while wearing the ring	I had minor discomfort while wearing the ring	I had moderate discomfort while wearing the ring	I had a lot of discomfort while wearing the ring	Other (comment below)
--	---	--	--	-----------------------

Comment: _____

2. How much did the ring affect you while performing day-to-day activities (circle answer option below)?

It did not affect me at all	It only affected me while performing certain activities	It affected me during all activities, but I could still do them	It prevented me from performing certain activities	Other (comment below)
-----------------------------	---	---	--	-----------------------

Comment: _____

3. After having worn the ring for a week, would you still choose to do ShangRing for circumcision, or would you choose surgery (circle answer option below)?

I would definitely choose ShangRing again	I would probably choose ShangRing again	I would probably choose surgery	I would definitely choose surgery	I don't know
---	---	---------------------------------	-----------------------------------	--------------

Comment: _____

(Survey is continued on next page)

4. How satisfied are you with the appearance of your circumcision (circle answer option below)?

I am very satisfied I am satisfied I am dissatisfied I am very dissatisfied I don't know

Comment: _____

5. At this point, would you recommend the ShangRing to someone you know who is considering circumcision (circle answer option below)?

Yes No I don't know at this time Other (Comment below)

Comment: _____

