 - A description of each adverse event by type, severity, time of detection (days post-application and/or post-removal) captured as date AE is diagnosed, clinical management, and resolution. The likelihood of relatedness to having undergone VMMC and relatedness specifically to the ShangRing device will be determined. AEs will be defined using the definitions in the second edition of the VMMC Adverse Event Action Guide.²⁴ These are specific to each AE type, but in general:
 - Mild: classification indicates minimal or no intervention is required beyond reassurance and observation;
 - Moderate: classification relates to those AEs that are neither mild nor severe, require intervention, and are usually managed on-site;
 - Severe: classification requires extensive intervention with referral or specialist input.
 - Note: a Serious Adverse Event (SAE) is a standard definition used across many types of interventions. In the context of VMMC, all AEs that meet criteria for severe should also be classified as SAEs. In addition, SAEs also include any event that:
 - Results in death

- Is life threatening
- Requires intervention to prevent permanent disability or incapacitation (including deformity), or results in permanent disability or incapacitation (including deformity)
- Requires hospitalization or referral to a specialist for higher level care or intervention.
- (Note: device displacement is included as an AE both in the moderate and severe classifications – see Appendix XV).

Secondary Endpoints

- Determine the training needed for proficiency, including number of procedures required under supervision to become certified as fully proficient. This will involve analyzing AE rates stratified by during training and post-training in addition to overall.
 - Determining whether various cadres are trainable as safe providers. This would involve analyzing AE rates stratified by provider cadre.
- Document client acceptability and satisfaction, to be measured by the following:
 - Time for client to return to normal activity, including work and routine tasks.
 - Clients' opinions of convenience (having device applied, 'wearing' the device for a week, and returning for device removal), acceptability, cosmetic result, and whether they would recommend VMMC, and specifically the ShangRing VMMC option to others.

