The primary focus of the acceptability component of the evaluation is to document attitudes towards and experiences with device circumcision (e.g., acceptability during the procedure and post-operatively during healing period while the device remains *in situ*), effects on activities of daily living, attitudes towards protection from HIV, effects on sexual satisfaction and/or penile sensation and behavior, pain, and satisfaction with cosmetic final result. Perceived acceptability of female partners will be assessed through male clients. The evaluation team will also collect data on reasons for not accepting the device by administering a brief survey to males declining participation in the evaluation (see Appendix XII). Provider acceptability will be assessed by exploring attitudes towards and experiences with device circumcision, impact of offering circumcisions on

clinical practice, barriers and facilitators of clinicians' implementation of device circumcisions (consistency of the final result, simplicity or ease of use).

All men (n=575) who are circumcised during the main implementation phase will be asked to answer a phone call to assess AEs three days post device removal (day 10). All men (n=575) will be asked to return for a follow-up visit on day 49 post-placement to assess healing. All men who are not clinically healed on the day 49 post-placement visit will be asked to return to the clinic at weekly intervals until healed. During the day 49 visit, and subsequent healing visits, men will also have their genital area photographed. A selection of 50 male clients will be asked to participate in private face-to-face qualitative interviews 28 days post-procedure. All clients returning for the day 49 healing assessment, and subsequent healing visits (and for clients under 18 a parent/guardian accompanying them), will be compensated a small amount for their travel costs and time (estimated to be between 7-10 USD/16,000-22,000 Tanzanian Shillings per visit, but not to exceed 30 USD/68,000 Tanzanian Shillings) total, as will clients selected for the face-to-face qualitative interviews (see Reimbursements section). As noted above, providers will be interviewed at the evaluations midpoint, at least after four weeks of client enrollment, and this interview will assess provider satisfaction with training, as well as provider acceptability.

Healing Component

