Data from the client's surgical and male circumcision medical records will be recorded on CRFs included in the Appendices (see Appendices VII and IX). The CRFs will be used to transfer the information collected in the performance of this evaluation to the clinical database. The original CRF will be kept in the clinic files and a copy will be maintained with additional documentation specifically for this evaluation including photographs, interviewer administered surveys and brief questionnaires. The hardcopy data will be entered into the evaluation database at each site. Corresponding forms, surveys and questionnaires will be completed immediately after each subject's visit. The site coordinator will review the CRFs for completeness and accuracy (signatures, dates, adverse events, serious adverse events, protocol departures) sign/date the forms where indicated. The evaluation team will retain originals of all source documents, subject consent forms, photographs and evaluation data as a permanent record.

The following data will be collected from clients receiving ShangRing circumcision:

Clinic Visit #1: Enrollment and Circumcision (Day 0)

- Documentation of general physical screening and medical examination on CRF
- Documentation of medication history on CRF
- Documentation of genital examination on CRF
- Documentation of device-related events and AE on forms, as needed
- Administration of evaluation survey after circumcision
- Collection of contact information from the client

Clinic Visit #2: Removal Visit (Day 7)

- Photographs of genitals after device removal
- Documentation of wound healing and genital examination on CRF
- Documentation of device-related events, AE and treatment and resolution of AE, as needed, on forms
- Documentation of changes to medical condition and medication on CRF
- Administration of evaluation survey after device removal

AE Assessment Phone Call (Day 10)

- Administration of an interview to determine whether client is experiencing signs and symptoms of an AE

Follow-Up In-Person Qualitative Interview (Day 28)

- For 50 clients
- Interview to determine client's feelings about ShangRing circumcision experience

Follow-Up In-Person Healing Assessment (Day 49)

- Documentation of wound healing and genital examination on CRF
- Photographs of genitals to document healing
- Documentation of device-related events, AE and treatment and resolution of AE, as needed, on forms

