Client acceptability, time to return to normal activity, and clients' satisfaction with the post-circumcision cosmetic results will be summarized from data recorded on the evaluation surveys and during qualitative interviews conducted with 10% of randomly selected clients. Similarly, provider acceptability will be summarized from data recorded during qualitative interviews conducted with providers. Qualitative interviews will be digitally recorded and then transcribed by qualified staff. The recordings will be transcribed according to the local language used and then to English. The recordings will not be marked with any identifying information but with a unique identifier. Transcriptions will be reviewed electronically, using a qualitative interview analysis software such as Atlas.ti or NVivo, and analyzed for themes. The analysis of the qualitative data will be done through an inductive process where categories are identified as they emerge. Opinions generated by the 10% of clients included in the interviews will be used to tailor the messaging for future program implementation.

The percentage of men healed by day 49, and the time at which all clients are healed, will be reported from data recorded on the client CRFs. The proportion of men unsuitable for ShangRing MC will be extracted from an evaluation log maintained for the purpose of documenting the number of ineligibles and the reasons for their exclusion. Similarly, the number of men who decline ShangRing or who withdrawal will be reported as a proportion.

The photographs taken to document healing and adverse events will be used to supplement the analysis of both endpoints. Photographs will be reviewed only by evaluation project staff, and used to enhance the understanding of different adverse events and as evidence of the duration of the healing process. Photographs of all adverse events (if the client consents) will also accompany the AE reporting, to provide further clarity on these events. The photos will also be used by project staff to better educate ShangRing providers.

Long-Term Data Storage

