Wants to be circumcised	Yes 	No 
Is uncircumcised	Yes 	No 
HIV sero-negative	Yes 	No 
Able to communicate in English or Swahili	Yes 	No 
Lives within 30 km of the facility	Yes 	No 
Agrees to be circumcised using the ShangRing device	Yes 	No 
Capable and willing to provide written informed consent (18 years and older), or written informed consent from parent (13-17 years)	Yes 	No 
If 13-17 years old, parent/guardian agrees to be present during circumcision (skip if client is older than 17)	Yes 	No 
Penis fits into one of the 18 ShangRing ring sizes	Yes 	No 
Able to understand the evaluation procedures and requirements	Yes 	No 
Agrees to abstain from sexual intercourse and masturbation, for six (6) weeks post removal (i.e., seven (7) weeks total)	Yes 	No 
Willing to provide valid contact information (i.e., telephone number, address of residence, place of employment and other locator information)	Yes 	No 
Has an activated cell/mobile phone or access to a cell/mobile phone	Yes 	No 
Agrees to complete brief evaluation surveys to assess satisfaction: post-placement and post-removal	Yes 	No 

Any "NO" answer disqualifies the subject from participating in the evaluation

Exclusion Criteria	(check appropriate box)	
Male below 13 years	Yes 	No 
Correct fitting ShangRing size is not available	Yes 	No 
Has the following diseases: hypospadias, hydrocele, scrotal hernia, balanitis, epispadias	Yes 	No 
Known bleeding/coagulation abnormality	Yes 	No 
Is cognitively impaired	Yes 	No 

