Date of ShangRing Device Placement (dd-mm-yyyy): _____

Contact Type (select one):

- **On-site visit (specify name of facility/site):** _____
- **Off-site visit (specify location, i.e. work, home, school):** _____
- **Phone contact (number called):** _____

Type of Visit (select one):

- Removal visit (specify days since device placement): _____
- Day 42 post-placement healing assessment (specify day if client comes in on different day): _____
- Post day 42 follow-up healing assessment (specify days since device placement): _____
- Unscheduled visit (specify days since device placement): _____

Is there a photographer present to take pictures of the procedure (circle one): Yes No

(If 'No,' do not proceed until a photographer is available. Photos must be taken with the photo frame, including client ID number, date and pain score before and after device removal).

Has there been a change to the client's medication since device placement (circle one): Yes No

(If 'Yes,' please record the medication on the medications CRF page).

Summary of Follow-Up:

Clinical course leading to client's visit today: _____

Care/advice provided:

Medication given (circle one)? Yes No

If yes, drug (name, dose and total quantity dispensed):

For removal visit, was anesthesia required during removal (circle one): Yes No NA (not removal visit)

If "Yes," what? _____

For removal visit, were there any device-related events or AEs that occurred during the removal (circle one):

Yes No NA (Device not removed this visit)

If "Yes," please record on Adverse Events form.

For removal visit, provider evaluation from 1 to 10 (1 being worst): _____

Name of provider who removed the ShangRing device: _____

Healing status observed by clinician (select one): Healed Not Healed NA (pre-day 42 visit)

Clinical healing defined as: clinical healing after MC by any method is intact epithelium (unbroken skin) covering the wound as judged by the provider on visual inspection, meaning that none of the following are present: sutures, scabbing, drainage, moisture, gaps between epithelial edges or ulceration.

Was client instructed not to masturbate until completely healed (select one)? Yes No NA (client healed)

Was client reminded to abstain from sexual intercourse until completely healed (select one)?

Yes No NA (client healed)

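### The only structured client rating of appearance is taken at device removal, before healing, and so does not match the stated aim of documenting satisfaction with the final cosmetic result

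*Protocol*

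**What the plan says.** The Acceptability Component, in the Implementation Phase section, lists "satisfaction with cosmetic final result" among the things the evaluation is to document. The Secondary Endpoints list clients' opinions on "acceptability, cosmetic result, and whether they would recommend VMMC", and Table 2 has an entry for cosmetic results under client acceptability.

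The Analysis Overview states that "satisfaction with the post-circumcision cosmetic results will be summarized from data recorded on the evaluation surveys", and names the qualitative interviews as a second source.

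Appendix XI, item 4, asks "How satisfied are you with the appearance of your circumcision". The Data Collection section places that survey at Clinic Visit #2 (day 7) as "Administration of evaluation survey after device removal". The screening form (Appendix VII) has clients agree to two surveys only: "Agrees to complete brief evaluation surveys to assess satisfaction: post-placement and post-removal".

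For the day 49 visit the Data Collection section lists the wound and genital examination, "Photographs of genitals to document healing", adverse events, and changes in condition or medication. It lists no client survey.

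**The concern.** A client's view of the final appearance can be given only once the wound has healed. The protocol asks its structured question when the ring has just come off, and does not ask it again at the visit where every client is called back to have healing judged.

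The evaluation is meant to inform ministry policy and the messages given to clients before the procedure. A satisfaction percentage from item 4, reported under the heading of cosmetic result, would be read as the client's verdict on the healed circumcision when it describes appearance at removal. The two could differ, and nothing in the documents indicates in which direction or by how much, so the difference could not be corrected afterwards. A separate statistical analysis plan could not repair this either, because no analysis recovers an answer that was never collected.

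**Working it through.** The plan gives no figure of its own on this point. The check is a trace of each client contact and form, followed by simple arithmetic.

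**Client contacts and what each asks about appearance or satisfaction with the result**

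| Contact | Instrument | Content on this point |
|---|---|---|
| Day 0 | Post-placement survey (Appendix X) | Reason for choice, placement, pain, recommendation; nothing on appearance |
| Removal, nominally day 7 | Post-removal survey (Appendix XI) | Item 4, a structured appearance rating |
| Day 10 call | Appendix XIV | Adverse event symptoms only |
| Day 28, 50 adults | Interview guide (Appendix XXII) | Open questions on satisfaction with the circumcision and its result (items 15 and 16) |
| Day 49 and weekly visits | Data Collection list; follow-up form (Appendix XII) | Examination, photographs, adverse events, medication; no client rating |

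**Healing status at the removal visit.** The follow-up form is used at every follow-up visit and reads "Healing status observed by clinician (select one): Healed Not Healed NA (pre-day 42 visit"). The form counts the healing visit as day 42 where the body text counts it as day 49 after placement. On either count, healing is recorded as not applicable at removal. The care instructions (Appendix XVII) tell clients to expect complete healing in three to four weeks or longer. The field study described under ShangRing and HIV+ Men gives 85.7% and 87.3% at 35-42 days. Read as proportions healed, these leave 100 - 85.7 = 14.3% and 100 - 87.3 = 12.7% not healed at that interval. The text does not say how many had healed earlier.

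**Timing**

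- Survey to healing assessment: 49 - 7 = 42 days.
- Interview to healing assessment: 49 - 28 = 21 days.

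**Coverage of satisfaction questions after removal**

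- Interviews as a share of the full cohort: 50/575 = 8.7%.
- Interviews as a share of the Phase 2 range in Table 2: 50/495 = 10.1% to 50/455 = 11.0%.
- Ages 13-17 are eligible for the evaluation but not for the interview.
- Structured appearance ratings planned at or after day 49: 0 of 575.

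**The case against.** The strongest case on the other side has five parts.

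1. *The formal endpoint does not say final.* That word appears only in the Acceptability Component. The Secondary Endpoints, Table 2 and the Analysis Overview speak of cosmetic result or results without a time point. This stands. The fault is a mismatch between one stated aim and the timing of the instrument, not a formally defined endpoint measured at the wrong time.

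2. *The interviews are a planned second source.* This also stands, and a reader who infers that cosmetic satisfaction goes unmeasured after removal would be wrong. Some men may have healed by day 28: three to four weeks counted from removal runs to day 7 + 21 = 28 through 7 + 28 = 35. But the answers are open-ended, come from 50 adults, and are not tied to an examined healing status. They cannot give the cohort's satisfaction with the healed result.

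3. *Late cosmetic information exists for everyone who attends.* Photographs are taken partly to document cosmetic results, and the adverse event table (Appendix XIX) has a scarring and poor cosmetic result category whose mild grade includes client complaints. Both are useful, but a complaint or a photograph is not a rating of satisfaction. Table 4 lists data collection from all men at 49 days, but the itemised list for that visit contains no survey.

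4. *Not every survey answer falls on day 7.* A reader might infer 575 answers on that day. The protocol does not fix this: removal can be on day 5 or 6 on request, can be later after tracing, or may not happen at the clinic, and clients may refuse any question. The correct description is the removal visit, nominally day 7.

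5. *A truthful label would be enough.* Calling the result appearance at removal would cure the reporting error without a new question. It would leave the stated aim unmet in the cohort, when the visit that could meet it is already scheduled.

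**Conclusion.** The point holds in a limited form. The only structured client rating of appearance is taken at the removal visit, about 42 days before healing is formally assessed, and does not measure satisfaction with the final cosmetic result. Later client opinion comes from 50 open-ended adult interviews, 8.7% of 575. No structured rating is planned at or after day 49.

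This rests on the appended forms and the itemised visit lists being the complete set of client instruments, and on 575 as the cohort size.

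The documents do not support saying that cosmetic satisfaction is not measured at all, that the day 7 answer is biased in a known direction, or that the whole secondary endpoint fails. This is one descriptive item within one secondary endpoint of a single-arm pilot. The adverse event endpoint, the sample size and the healing endpoint are untouched. It is worth changing because the change is cheap and lets the evaluation answer a question it sets itself.

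**What to change.** - Repeat Appendix XI item 4, unchanged, at the day 49 visit. For men not healed then, repeat it at the weekly visit where healing is recorded.
- Add the item to the day 49 and additional-visit lists under Data Collection and to the follow-up form (Appendix XII), and amend the screening form (Appendix VII), which now names two surveys only.
- Report the answer from the visit where healing is recorded as satisfaction with the final cosmetic result, stating how many responded. Report the removal-visit answer separately as early appearance.

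Items 3 and 5 of Appendix XI need not be repeated for this purpose: they ask about choosing the device again and recommending it, and item 3 is worded for one week of wear.

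The cost is one extra question at a visit already scheduled and reimbursed, plus small form changes. Some answers will be missing, because a client who does not attend on day 49 is classed as lost to follow-up and missed visits other than removal are normally pursued by phone or text only. That is why the number responding must be shown.
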